1. BACKGROUND AND RATIONALE

1.1 Management of Resistant Acute Myeloid Leukemia (AML)

Patients with AML who fail induction chemotherapy (refractory) and those who relapse after optimal chemotherapy are seldom cured with salvage regimens (6). While allogeneic stem cell transplantation can cure 30-50% of patients with resistant AML who are transplanted in complete remission (CR), most patients are not candidates due to failure to achieve CR with salvage therapy or due to comorbid conditions or absence of a suitable donor.

Given that resistance to chemotherapy is the major cause of death for patients with AML, there is an urgent need for novel treatment regimens that are well tolerated and capable of overcoming disease resistance (7). Recent advances in molecular genetics have revealed that AML is characterized by a complex, sub-clonal architecture that evolves spontaneously and in response to treatment. Chemotherapy-resistant leukemia clones can quickly become dominant by “survival of the fittest” dynamics. In order to target minor, yet resistant clones, one strategy is to augment the effectiveness of current chemotherapeutic agents.

1.2 Etoposide (VP-16) in AML

Etoposide is a semisynthetic glucoside derivative of podophyllotoxin. Although the exact mechanism of action is uncertain, it is generally accepted that etoposide acts as a Topo II inhibitor triggering decatenation checkpoint arrest (2). Although intravenous etoposide has activity in a variety of hematologic malignancies and solid tumors, the drug has usually been combined with other active agents so that the contribution of etoposide to efficacy or toxicity is difficult to assess (8-11). However, high-dose single-agent etoposide is clearly active in patients with hematologic malignancies although toxicity is severe (12).

Oral etoposide was developed to facilitate outpatient therapy. In addition, available data suggests schedule dependency for etoposide such that administration on multiple consecutive days may be more effective than dosing at 6 to 8 day intervals (13). Availability of oral etoposide permits prolonged exposure without multiple office visits. Perhaps the largest experience using single agent oral etoposide in patients with hematologic malignancies was reported by Osby et al (14). In that trial etoposide was given at a fixed dose of 100 mg daily for 14 days in 21 day cycles. As expected, myelosuppression was the major toxicity with approximately 2/3 of all patients experiencing grade 3/4 neutropenia. Of 13 patients with AML (11) or myelodysplasia (2), 5 received a single course due to severe, primarily hematologic toxicity. Non-hematologic toxicity included grade 2 hepatic dysfunction in 2/14 evaluable patients, grade 1 renal dysfunction in 1/11 patients and grade 3 nausea/vomiting in 2/14 patients. This toxicity profile is similar to that described by others following treatment with multiple daily doses of oral etoposide with the exception of mucositis described with 21 day schedules (13).

In conclusion, oral etoposide is an active and well tolerated agent for treatment of resistant AML and offers the convenience of treatment in the outpatient setting.

1.3 Metnase: A DNA Repair Component Mediates Resistance to Topo II Inhibitors

DNA double strand breaks can be generated by failed decatenation and Topoisomerase II α (Topo II) is the critical decatenating enzyme (2). Topo II inhibitors, such as etoposide, can trigger decatenation checkpoint arrest at either of 2 decatenation mitotic checkpoints. Metnase (also

SETMAR) is a novel DNA repair protein with a SET histone methylase domain and a transposase nuclease domain and both are essential for enhancement of DNA double-strand break repair. Hromas et al reported that both AML and ALL cells fail to arrest in mitosis when Topo II is inhibited and that Metnase levels mediate progression through mitosis by enhancing Topo II function. Critically, Metnase mediates cell proliferation through and protects Topo II from etoposide. This implies that Metnase is a critical mediator of leukemia resistance to the cytotoxic effect of Topo II inhibitors (1).

Based on these observations, inhibition of Metnase could overcome the resistance of leukemia cells to Topo II inhibitors. Small molecule inhibition of Metnase should show an excellent therapeutic index given that it is overexpressed in malignant cells and that there are few other human Transposase domain proteins with which to cross-react. Hromas et al virtually screened a large chemical library of small compounds for docking in the into the Metnase nuclease active site (4). It was found that high but clinically achievable concentrations of ciprofloxacin blocked the ability of Metnase to cleave DNA, which is essential for its ability to repair DNA double-strand breaks. Further, ciprofloxacin enhanced the antiproliferative effects of etoposide on the AML cell line KG-1(4).

In summary, ciprofloxacin is a Metnase inhibitor which enhances the antiproliferative effect of etoposide on AML cells in-vitro. These observations indicate that ciprofloxacin could improve the effectiveness of etoposide in the treatment of resistant AML.

1.4 Proposal: Treatment of Resistant AML with Etoposide and Ciprofloxacin

This protocol proposes to treat patients with resistant AML using the combination of etoposide and ciprofloxacin. In the Phase Ib portion of this trial, the maximum tolerated dose will be determined of ciprofloxacin when given in combination with a fixed dose of etoposide. The protocol will then proceed with the Phase II portion, in which the activity of this combination will be determined in patients with resistant AML.

2. OBJECTIVES

2.1 Primary

In subjects with resistant AML, to

Phase Ib: Establish the maximum tolerated dose (MTD) of oral ciprofloxacin when given in combination with a fixed dose of oral etoposide.

Phase II: Determine the rate of CR (See [Appendix A](#)) following treatment with the MTD (15).

2.2 Secondary

In subjects with resistant AML, to

- Determine the safety and feasibility of treatment with ciprofloxacin and etoposide;
- Measure the response duration, progression-free and overall survival (PFS and OS respectively);
- Estimate the incidence of Grade ≥ 3 adverse events following treatment with ciprofloxacin and etoposide at the MTD.

3. STUDY DESIGN

3.1 Overview

This is an open label, single arm, phase Ib/II study of oral ciprofloxacin and etoposide in subjects with resistant AML. In the Phase Ib portion of the study, the MTD of ciprofloxacin will be determined using a standard 3+3 design. In the Phase II portion the rate of CR will be estimated following treatment with a fixed dose of etoposide given with the MTD of ciprofloxacin. For both study phases, all subjects will receive 1 cycle of induction. At the end of Cycle 1, subjects who demonstrate progressive disease will have completed study treatment. For any subject who demonstrates stable disease or a partial response, a second cycle of induction will be given. No subject will receive more than 2 cycles of induction.

3.2 Rationale for Drug Doses and Schedule

3.2.1 Etoposide

As discussed in Section 1.2, oral etoposide is an active agent in the treatment of AML. Etoposide absorption is saturable at doses > 200 mg/day. Lower doses are associated with increased bioavailability but with higher inter- and intra-subject variability (16). In the current study etoposide will be administered at a daily dose of 200 mg in order to optimize bioavailability. As discussed above, the use of 14 day cycles of oral etoposide resulted in toxicity which limited therapy to a single cycle in over 1/3 of those treated (14). In order to give multiple cycles of therapy 7-day courses of etoposide will be administered.

3.2.2 Ciprofloxacin

Ciprofloxacin is a quinolone antibiotic which works by inhibiting DNA gyrase (17, 18). Ciprofloxacin is a Topo II inhibitor and in-vitro and xenograft tumor models have shown that this drug has anti-proliferative and possibly pro-apoptotic activity (19-23) at concentrations ranging from 12-800 mcg/ML (19, 20, 23-27). The use of ciprofloxacin in the current trial is based on the ability of this drug to inhibit Metnase and thereby enhance the activity of etoposide in subjects with resistant acute leukemia. Hromas et al demonstrated that ciprofloxacin potentiated the activity of etoposide on AML cell lines at a concentration of 2 µmol/L (0.662µg/mL based on its molecular weight of 331) (4).

Per the prescribing information, a single dose of 250 mg, 500 mg, 750 mg, and 1000 mg of oral ciprofloxacin in healthy volunteers achieved a C_{max} of 1.2, 2.4, 4.3 and 5.4 µg/mL (28). The elimination half-life of ciprofloxacin is 4 hours, and PK studies have shown the mean serum concentrations at 12 hours after a single dose of 250 mg, 500 mg, and 750 mg were 0.1, 0.2 and 0.4 µg/mL, respectively.

The 750 mg twice daily as a starting dose was chosen because this dose results in sustained levels that approximate those shown to augment etoposide effect ([See Table 2](#)) (4). Further, this dose is commonly used for treatment of infection and has been well tolerated (28). To achieve a steady state concentration prior to initiation of etoposide, ciprofloxacin will be started 24 hours before etoposide is begun. If the starting dose of ciprofloxacin is tolerated, a higher dose of 1,000 mg twice daily will be explored in order to further increase ciprofloxacin 12 hour levels. Although less commonly used, this dose has also been well tolerated in studies in normal volunteers and in subjects with infection (29, 30).

3.3 Phase Ib

3.3.1 Dose Escalation and De-Escalation

The dose escalation phase of the study will utilize a standard “3+3” design to establish the MTD of oral ciprofloxacin in combination with a fixed dose of etoposide (200 mg daily on days 2-8). Ciprofloxacin will be given on days 1-10 at one of three dose levels shown in [Table 2](#). The MTD will be defined as the level associated with a < 1/3 chance of DLT. To summarize: (See [Figure 1](#))

- 1) Three subjects are initially treated at dose Level 0 (ciprofloxacin 750 mg twice daily).
 - a) If none of these experience DLT, then dose will be escalated to Level +1.
 - b) If one of these experiences DLT, then up to three more subjects are treated at Dose Level 1. If one or more of these develops DLT, then the MTD is considered to be exceeded and dose will be reduced to Level -1. If none of these additional subjects develop a DLT then the dose will be escalated to Level +1.
 - c) If 2/3 of these subjects experience DLT, then the MTD is considered to be exceeded and dose is reduced to Dose Level -1.
- 2) If the dose is escalated to Dose Level +1, the same process will be followed to determine if this is the MTD (no further escalation).
- 3) If the dose is reduced to Level -1, then the same process will be followed to determine if this is the MTD. If Dose Level -1 is above the MTD the study will be closed and it will be concluded that treatment with this combination at effective doses is not safe.

Table 2. Planned Dose Levels

Dose Level	Drug	Dose	Frequency	Schedule
0	Ciprofloxacin Etoposide	750mg 200mg	Twice Daily Once Daily	D1-10 D2-8
+1	Ciprofloxacin Etoposide	1000mg 200mg	Twice Daily Once Daily	D1-10 D2-8
-1	Ciprofloxacin Etoposide	500mg 200mg	Twice Daily Once Daily	D1-10 D2-8

[figure not shown]
Subjects withdrawn before Cycle 1 Day 1 (C1D1) will not be evaluable for dose escalation decisions and will be replaced in their treatment cohort. A subject is evaluable for dose-escalation decisions provided: they receive all drug doses and remain on study until evaluation at Cycle 1 Day 28 without a DLT; or they experience a DLT during Cycle 1. Subjects who miss any etoposide or ciprofloxacin doses or withdraw from study without a DLT and prior to Cycle 1, day 28 are not evaluable for dose escalation decisions and will be replaced in their cohort of treatment.

No more than 3 subjects will be added simultaneously to a dose cohort during dose escalation. The Phase Ib portion of this study ends when the MTD has been identified.

Subjects entered during Phase 1b who develop DLT with the first cycle will be withdrawn from the study. Subjects who do not develop DLT with the first cycle, will be treated in a second repeated 28-day cycle with ciprofloxacin and etoposide at the dose level given during Cycle 1

until completion of Cycle 2, disease progression, unacceptable toxicity, consent withdrawal, PI decision to discontinue treatment, or termination of the study. Intra-subject dose escalation will not be permitted. No subject will receive more than 2 cycles of treatment.

Figure 1. Example of How MTD Will Be Determined in Cycle 1

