Phase Ib:

In the **Phase Ib** portion of the study, subjects will be enrolled in cohorts of three (3) in a traditional 3+3 study design (5). The starting dose is level “0” and includes: ciprofloxacin 750 mg orally twice daily on Days 1 - 10 and etoposide 200 mg orally once daily on Days 2 – 8. During the first cycle of treatment, subjects will be individually assessed for safety and dose limiting toxicity (DLT) for the purpose of determining the MTD of ciprofloxacin. The MTD will be defined as the highest dose of ciprofloxacin at which < 33% of the subjects treated at a given dose level experience a DLT (See [Figure 1](#)). The **Phase Ib** portion of this study ends when a MTD is identified among the three planned dose levels (See [Table 2](#)).

Subjects withdrawn before Cycle 1 Day 1 (C1D1) will not be evaluable for dose escalation decisions and will be replaced in their treatment cohort. A subject is evaluable for dose-escalation decisions provided: they receive all drug doses and remain on study until evaluation at Cycle 1 Day 28 without a DLT; or they experience a DLT during Cycle 1. Subjects who miss any etoposide or ciprofloxacin doses or withdraw from study without a DLT and prior to Cycle 1 Day 28 are not evaluable for dose escalation decisions and will be replaced in their cohort of treatment.

During dose escalation no more than 3 subjects will be treated simultaneously at any given dose level. The **Phase Ib** portion of this study will not be complete until > 28 days after accrual of the last subject.

Phase II:

Enrollment in the **Phase II** portion of the study will begin once the MTD has been determined. After Cycle 1, subjects with progressive disease will be removed from the study. Other study participants will continue to receive a second 28-day cycle of ciprofloxacin and etoposide at the MTD or until one of the following occurs: disease progression, unacceptable toxicity, consent withdrawal, completion of Cycle 2, or termination of the study.

Dose Limiting Toxicity (DLT)

DLT will be defined as any of the following events that are considered to be related to treatment with ciprofloxacin and etoposide. For the purpose of dose-escalation and MTD determination, only DLTs that occur during the first cycle of oral ciprofloxacin and etoposide will be considered. These include:

1. Any Grade \geq 3 non-hematologic toxicity, except alopecia; and vomiting or nausea uncontrolled by medical management;

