4.1 Etoposide and Ciprofloxacin

Ciprofloxacin will be administered orally twice daily on Days 1 to 10 of each 28-day cycle. Whenever possible, doses should be taken at 0800 hours and 2000 hours. If for some reason the doses are not taken at these times, ciprofloxacin can be taken as late as 6 hours after the scheduled time. If > 6 hours elapses, that dose of ciprofloxacin will be held and not made up. The starting dose will be 750 mg (dose level 0) with escalation to a maximum of 1000 mg (dose level +1) or de-escalation to a minimum of 500 mg (dose level -1).

Etoposide at a fixed dose of 200 mg will be administered orally once daily on Days 2 to 8 of each 28-day cycle. Subjects will be instructed to take etoposide with their morning dose of ciprofloxacin at 0800 hours on an empty stomach. If for some reason the dose is not taken at this time, it may be taken as late as 6 hours after the scheduled time. If >6 hours elapses, that dose of etoposide will be held and not made up.

A medication diary will be given to all subjects and they will be instructed to record the actual times they take both etoposide and ciprofloxacin. Doses missed will be recorded as such. Subjects will be told to call within 12 hours of missing a dose. Subjects will be instructed to bring the diary and any unused medication with them to all study visits. Any unused medication will be disposed of per institutional standard practice.

Subjects in Cycle 1 of Phase Ib who miss any etoposide or ciprofloxacin doses will be considered evaluable only if a DLT occurs. Otherwise they will be removed from the study on Day 28 and replaced in the cohort in which they were treated. Subjects in Phase Ib beyond the first cycle and those in Phase II will be considered evaluable for response if they have received at least one cycle in accord with the protocol. For these subjects non-compliance with dosing will be dealt with at the discretion of the PI.

Standard administration instructions will be given to each subject for ciprofloxacin (*e.g.*, separating administration from dairy products, calcium-fortified juices, sucralfate, antacids, or other medications that contain aluminum, magnesium, calcium, iron, or zinc). Subjects will be advised not to consume grapefruit or grapefruit juice within 7 days prior to starting ciprofloxacin and until 7 days after completion of all doses of ciprofloxacin on study.

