14.4 Appendix D: Statistical Characteristics of the “3+3” Design

Probabilities of Stopping or Continuing Dose Escalation for Given Probabilities of DLT Associated with the Dose Level

True Probability of DLT at a Dose Level	0.05	0.1	0.2	0.33	0.4	0.5	0.6	0.67	0.7	0.8
Probability of Dose Escalation Based on 3 or 6 Subjects (2 or more DLTs)	0.97	0.91	0.71	0.43	0.31	0.17	0.08	0.04	0.03	0.01
Probability of Ceasing Dose Escalation Based on 3 or 6 Subjects (2 or more DLTs)	0.03	0.09	0.29	0.57	0.69	0.83	0.92	0.96	0.97	0.99
Probability Based on only 3 Subjects (0 DLT)	0.86	0.73	0.51	0.30	0.22	0.13	0.06	0.04	0.03	0.01

Key: DLT = dose limiting toxicity

The probability that dose escalation will cease is at least 92% when the DLT probability is > 60%. If the true probability of DLT for a dose level is at least 33%, the probability of stopping dose escalation is at least 57%. If the true probability of DLT for a dose level is less than 10%, the probability of stopping dose escalation is less than 10%. The probability of dose escalation continuing is at least 91% when the DLT probability is < 10%.

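### Step 1(b) of the Phase Ib escalation rule places the expansion subjects at a dose level that the protocol does not define, and it must be reconciled with the rest of the design

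*Combined protocol and SAP*

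**What the plan says.** Section 3.3.1 announces the design: "The dose escalation phase of the study will utilize a standard “3+3” design to establish the MTD of oral ciprofloxacin". The first cohort is fixed in step 1: "Three subjects are initially treated at dose Level 0 (ciprofloxacin 750 mg twice daily").

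Step 1(b) covers one DLT among those three: "If one of these experiences DLT, then up to three more subjects are treated at Dose Level 1". Two outcomes follow in the same step. For any further DLT: "If one or more of these develops DLT, then the MTD is considered to be exceeded and dose will be reduced to Level -1". For none: "If none of these additional subjects develop a DLT then the dose will be escalated to Level +1". Steps 2 and 3 do not restate the rule for Levels +1 and -1; they apply the step 1 process by reference.

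Table 2 lists three levels, 0, +1 and -1. Section 4.1 uses the same signed labels: "The starting dose will be 750 mg (dose level 0) with escalation to a maximum of 1000 mg (dose level +1"), with -1 as the minimum. A level called plain 1 appears in neither place.

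Three other places bear on the step:
- Section 3.2.2 makes exploration of the higher dose conditional on the starting dose being tolerated.
- The Synopsis (Phase Ib) defines the MTD as the highest dose at which "< 33% of the subjects treated at a given dose level experience a DLT".
- Appendix D tabulates the design's behaviour by true DLT rate at a dose level, for example "Probability of Ceasing Dose Escalation Based on 3 or 6 Subjects (2 or more DLTs").

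**The concern.** The sentence that decides what happens after a first DLT points to a level that does not exist in the protocol's own table. The nearest defined label is +1. On that reading, zero DLTs in the added subjects would lead to escalation to the level they had just received. One or more DLTs would send the study to Level -1 because of toxicity seen at +1, passing over Level 0. The verdict would rest on three subjects at each of two doses, whereas the MTD definition and Appendix D both work level by level.

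This matters for two reasons. The sentence governs dosing straight after a toxicity event. It also drives the Phase Ib primary objective, and the MTD found there is carried into Phase II. Because steps 2 and 3 borrow the process from step 1, a fixed but undefined label travels with it to the other levels.

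**Working it through.** **Inputs.** The decision rule comes from Section 3.3.1, and the true DLT rates and stated probabilities come from Appendix D. Let p be the true DLT rate for the first three subjects and q the rate for the added three. The documents give no expected DLT rate for any level, so the values of p and q in steps 2 to 4 are assumptions. Step 1(c) mentions only two DLTs of three; three of three is treated the same way.

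**1. Reproduce Appendix D.** With all subjects at one level (q = p):

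P(escalate) = (1−p)³ + 3p(1−p)² × (1−p)³

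| p | Appendix D | Computed |
|---|---|---|
| 0.05 | 0.97 | 0.973 |
| 0.10 | 0.91 | 0.906 |
| 0.20 | 0.71 | 0.709 |
| 0.33 | 0.43 | 0.434 |
| 0.40 | 0.31 | 0.309 |
| 0.50 | 0.17 | 0.172 |
| 0.60 | 0.08 | 0.082 |
| 0.67 | 0.04 | 0.044 |
| 0.70 | 0.03 | 0.032 |
| 0.80 | 0.01 | 0.009 |

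All ten agree to two decimals. The appendix therefore assumes that both groups of three share one DLT rate.

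**2. How often step 1(b) is reached.** P(exactly 1 of 3) = 3p(1−p)²:
- p = 0.10: 3 × 0.10 × 0.81 = 0.243
- p = 0.20: 3 × 0.20 × 0.64 = 0.384
- p = 0.33: 3 × 0.33 × 0.4489 = 0.444

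**3. Chance of being sent to Level -1, once in step 1(b).** This is 1 − (1−q)³. With one common rate of 0.20 it is 1 − 0.512 = 0.488. Under the +1 reading:
- q = 0.33: 1 − 0.301 = 0.699
- q = 0.40: 1 − 0.216 = 0.784
- q = 0.50: 1 − 0.125 = 0.875

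**4. Overall probability of escalation under the +1 reading.** P = (1−p)³ + 3p(1−p)² × (1−q)³. With p = 0.20:
- q = 0.20 (common rate): 0.512 + 0.384 × 0.512 = 0.709
- q = 0.33: 0.512 + 0.384 × 0.301 = 0.628
- q = 0.40: 0.512 + 0.384 × 0.216 = 0.595
- q = 0.50: 0.512 + 0.384 × 0.125 = 0.560

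The fall is 8 to 15 percentage points. For other assumed starting rates:
- p = 0.10: 0.906 becomes 0.853 (q = 0.20) or 0.802 (q = 0.33).
- p = 0.33: 0.434 becomes 0.397 (q = 0.40) or 0.356 (q = 0.50).

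**5. The text side by side.** The two outcome sentences of step 1(b) treat both +1 and -1 as destinations still to be reached after the added subjects have been observed. An expansion at +1 collides with the zero-DLT sentence, and one at -1 would collide with the other. The label therefore cannot be settled by supplying a missing sign.

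**The case against.** The best defence is that this is a slip that the surrounding text exposes. The +1 reading cannot be carried out coherently. The design is called a standard 3+3, the MTD is defined within a level, and Appendix D was computed correctly for expansion within one level. The label could be a leftover from a numbering in which the starting level was 1. Figure 1, which the section cites as illustrating the MTD decision, is not shown in the text available here and may display the expansion level plainly.

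Most of this stands, and it limits what may be claimed. A reader might infer:

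- **That the protocol orders the higher dose after a DLT.** It does not say so. The label carries no sign, and equating it with +1 is an inference.
- **That Appendix D is wrong or cannot be used.** It is arithmetically right for the design it describes. It fails to describe the trial only if the added three have a different DLT rate.
- **That neither level could ever have six subjects behind it.** Even under the +1 reading, step 2 could bring more subjects at +1.
- **That 1000 mg is wholly untested.** Section 3.2.2 cites tolerability in volunteers and in subjects with infection; what is untested is this combination.
- **That the effect is as large as 0.78 against 0.49.** That contrast is conditional on reaching step 1(b) and uses one assumed pair of rates (20% and 40%). Unconditionally, the same pair gives 1 − 0.595 = 0.405 against 1 − 0.709 = 0.291, about 11 points.

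The defence does not remove the defect. In the text available, step 1(b) is the only wording of the expansion rule, and the Synopsis does not repeat it. If Figure 1 shows something different, the protocol holds two instructions. A dosing rule should not depend on staff working out that its literal text is a mistake.

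**Conclusion.** The point holds as an internal contradiction in an operative dosing rule. Step 1(b) names an undefined level. Its nearest reading conflicts with the rest of the step, Section 3.2.2, the MTD definition and the basis of Appendix D. A labelling error is the probable explanation, and the documents do not support a claim that subjects would in fact be misdosed.

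The branch is not rare: 24%, 38% or 44% of the time at true Level 0 rates of 10%, 20% or 33%. If the +1 reading were followed, with assumed rates of 20% at Level 0 and 33–50% at +1, the chance of being sent to Level -1 within the branch would be 0.70–0.88, against 0.49 with one common rate. Overall escalation would be 0.56–0.63 against 0.71. These sizes depend on assumed rates and on a reading that is itself an inference. The need for correction depends on neither, because the rule decides dose after a DLT and the Phase Ib MTD.

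**What to change.** The sponsor should reconcile the level named in step 1(b) with Table 2, the other sentences of step 1(b), steps 2 and 3, Figure 1, the Synopsis MTD definition, Sections 3.2.2 and 4.1, and Appendix D. One unambiguous level from Table 2 should be stated for the expansion subjects, and it should be clear how the step reads when steps 2 and 3 reuse it at the other levels. No view is taken here on which dose is right.

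The cost is a one-line protocol correction and a check of Figure 1, with no added subjects or procedures. Appendix D needs no recalculation if the reconciled rule keeps all 3 or 6 subjects at one level; otherwise its figures would have to be recomputed.
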